### 6.1 General Study Agents considerations

#### 6.1.1 Plasmid

The plasmid DNA vector encodes CD74 anchored to pre-proinsulin (PPI) in a multi-cistronic expression construct. The autoantigen PPI is expressed followed by a 2A peptide element with TGF-β1, an IRES element, IL-10, a subsequent 2A element, and terminal IL-2. The vector will be delivered via subcutaneous injection as outlined in the treatment schedule.

#### 6.1.2 Vector Considerations:

Plasmid therapies have been proposed and tested clinically in a number of indications (PMID: 30445702). While the pre-clinical animal model studies suggest the drug will be safe and result in transient vector responses (see IB for additional information), there remains a potential that a plasmid-based dsDNA vector may induce some host inflammatory response as a function of innate sensing machinery (e.g., as a PAMP/DAMP via TLRs). Moreover, there is a possibility that the inclusion of 2A elements may alter the structure of transgenes. It is currently unknown if this could result in an immune response to the native proteins and/or modified epitopes.

### 6.1.3 Drug Considerations:

NNC0361-0041 is intended to be injected without adjuvants or enhancers and therefore is expected to only transfect and express in a limited number of cells. The systemic exposure to plasmid-derived proteins will therefore be minimal and occurrence of acute safety signals is consequently considered unlikely.

#### Autoantigen (Pre-proinsulin)

Rationale: The goal is use host machinery to express ectopic transgenes and facilitate the presentation of PPI peptides in the context of MHC class I and II molecules to host T cells via endogenous antigen processing and presentation machinery. The hypothesis is that both CD4+ and CD8+ T cell responses will be impacted, with the net effect of shifting the balance to favor immune regulation. Potential side-effects may include a delayed hypersensitivity reaction at the injection site or in any site the drug and transgene may ultimately be expressed. While the expectation is that endogenous Tregs will be induced in response to the drug, mechanistic and clinical data will also monitor the potential for the transgene to induce the expansion and/or activation of effector cells that might accelerate beta cell loss.

### 6.1.4 Immunomodulatory Agents:

### Transforming Growth Factor – Beta 1 (TGF-β1)

TGF- $\beta$ 1 is a pleiotropic polypeptide that is known for its capacity to function as a negative growth factor to limit T cell proliferation. TGF- $\beta$ 1 is naturally processed by proteolytic activation into its active form that signals through TGF- $\beta$ 1 receptor. On-target implications of localized TGF- $\beta$ 1 are expected to include the induction of both CD25 and FOXP3 in T cells following TCR ligation with reduced effector responses and proliferation. In excess, TGF- $\beta$ 1 can cause tissue remodeling, with reports of renal fibrosis following systemic exposure to high levels of active TGF- $\beta$ 1. Given the receptors for TGF- $\beta$ 1 are widely expressed throughout the innate and adaptive immune system, TGF- $\beta$ 1 can lead to broad immunoregulation, including the downregulation of MHC II expression and costimulatory molecules on host APCs. While no agents are expected to induce mutations or

DNA damage, TGF- $\beta$ 1 signaling has previously been associated with transformation and epithelial-mesenchymal transition (EMT), a process that is favored in tumor cells and facilitates migration and invasion.

Protocol Version: Jan 7, 2022

### Interleukin-10 (IL-10)

Interleukin-10 is most often regarded as an anti-inflammatory class II cytokine capable of inducing a tolerogenic Dendritic Cell (DC) phenotype and subsequent Tr1-like cell response. IL-10 is thought to autoregulate its own expression through the IL-10R and inhibition of p38 signaling. As with TGF- $\beta$ 1, IL-10 exerts a broad array of pleiotropic functions on host and immune cells. Of note, IL-10 is recognized for its capacity to suppress host responses to TLR ligands such as LPS in myeloid lineage cells. Locally, IL-10 has been reported to be produced by mast cells, potentially attenuating the inflammatory byproducts of these cells that may act locally at the injection site. In general, IL-10 suppresses innate inflammation, but can also induce inflammatory subsets at high concentrations. In pegylated forms, IL-10 induces markers associates with T cell activation including PD-1, Lag3, FasL and decreased serum TG $\beta$ b. Thus, IL-10 is most often regarded as an immunoregulatory cytokine in the context of myeloid exposure to PAMPs but may induce immune activation in a transgene form.

### Interleukin-2 (IL-2)

Interleukin-2 is commonly regarded as a T cell growth factor and binds to the high-affinity trimeric IL-2R composed of the common gamma chain (CD132), IL2 beta chain (CD122), and the high affinity alpha chain (CD25). Importantly, the high-affinity trimeric IL2R is constitutively expressed on  $T_{\text{regs}}$  but can be upregulated on activated conventional T cells. In  $T_{\text{regs}}$ , IL-2 binding the IL2R induces pSTAT5 signaling and reinforces FOXP3 expression and  $T_{\text{reg}}$  fitness. In excess, IL-2 can induce injection site reactions, changes in vascular permeability, localized inflammation, and when present in high concentrations, bind the intermediate affinity IL2R expressed on innate lymphoid cells, NK cells, and conventional and effector T cell subsets. TCR ligation, TGF- $\Box$ 1 signaling, and co-stimulation are known to upregulate CD25 on T cells and early IL-2 signaling is reported to suppress Th17 cell differentiation.

#### 6.2 Potential Risks

Based on literature, hypothesized mechanism of action and the inherent potential for reactions when introducing foreign matter into the subcutis, the following risks are currently considered potential risks for human subjects.

#### 6.2.1 Acceleration of Beta Cell Destruction

While the plasmid vector is aimed to provide antigen specific tolerogenic therapy, and no evidence of immune activation was seen in preclinical studies, unintentional acceleration of beta cell destruction due to immune activation is a potential risk, which will be monitored through scheduled assessments of insulin secretion by MMTT.

# 6.2.2 Hypersensitivity, Allergic, and Injection site reactions

Plasmid therapy is generally well tolerated and the DNA component is not considered to be immunogenic. Plasmid DNA vaccines have been evaluated in many clinical trials, and anaphylaxis has not been reported. The safety and tolerability of DNA plasmid vaccines has been evaluated in several clinical trials, both for autoimmune diseases where the plasmids expressed autoantigens (45) and for anti-viral responses (46), in both cases with repeated dosages. As summarized in a review article, multiple studies have reported the DNA platform to be well tolerated and to have a very good safety record (47,48).

It is noteworthy, that while anaphylactic reactions have been observed on occasion with subcutaneous or intradermal administration of peptides in mice as well as humans (49), such anaphylactic reactions have not been observed with DNA vaccines. This includes plasmid DNA administration in conjunction with cytokine response modifiers as well as other adjuvants for which, unlike peptide therapy, anaphylaxis has not been observed. Cytokine modulators have been analyzed in the past, and skewing of immune responses towards allergic pathways (but not anaphylaxis) can occur by using IL-4 and II-5 (50). This is in contrast to the cytokines expressed by our plasmid, which were carefully chosen to induce tolerance in both TH1 (more the anti-viral and autoimmune effector responses) and TH2 (more the allergic responses) and thus not enhance any type of allergic (more TH2-like) response.

Further, an innate, immediate type 1 reaction should not be increased with this plasmid compared to others, and repeated administrations are not believed to be able to provoke such a response. In pre-clinical studies in mice and monkey with repeated dosing of the plasmid, importantly no anaphylactic or other allergic reactions have been demonstrated (see IB Appendix 1 for an overview of all non-clinical studies performed). The longest study conducted in monkeys with NNC0361-0041 is the 13 week GLP toxicity study. Monkeys were dosed once weekly with either vehicle, 4 or 20 mg NNC0361-0041 plasmid/animal (approximately 1 and 5 mg plasmid/kg) for 13 weeks followed by either 8 or 13 weeks recovery. Animals were observed after each dosing for clinical signs and no adverse reactions were observed. In particular, no anaphylactic reactions were observed. In the study, cytokines (IL-1β, IL-2, IL-4, IL-6, IL 8, IL-10, IL-12p40, IL-15, TGFβ-1, IFN-γ and TNF-α) were also measured (pre-study, 2 h post dose after first and 4th dose and at end of study) and no changes were observed. Mouse surrogate plasmid has been dosed thrice weekly and up to once daily in mice without any signs of anaphylaxis.

Evaluation of plasmid exposure in the 13 week toxicity study in non-human primates has demonstrated that plasmid exposure declines to levels below LLOQ within a week after dosing. Thus, with the planned weekly dosing, accumulation is not anticipated in this study, meaning that exposure will not increase as participants are dosed repeatedly for the 12 weeks.

Thus, while individuals may experience systemic or local adverse effects shortly after drug administration including hypersensitivity, or allergic reactions, this is not considered to be a likely effect of this therapy. Injection site reactions may also occur. All subjects will be closely monitored, and injection sites will be carefully assessed for local reaction and fibrosis at each study visit. Proinflammatory cytokines will be monitored in response to plasmid injection.

#### 6.3 Protecting Against or Minimizing Risks.

#### 6.3.1 Infectious Disease

The plasmid vector is aimed to provide antigen specific local tolerance and not broad immunosuppression. Thus, while the potential for infection will be carefully monitored with clinical and laboratory assessments, adverse events associated with infectious diseases are not expected.

#### 6.3.1.1 COVID-19

Risk of COVID-19 infection in relation to participation in trial:

Key risk factors for adverse outcomes of COVID-19 infection appear to be old age, particularly in combination with cardiovascular co-morbidity, obesity, cancer or compromised immune system.

The plasmid vector is not expected to increase the risk of COVID-19, but patients may be exposed to the risk of COVID-19 transmission and infection in relation to site visits if an outbreak is ongoing.

The risk of COVID-19 transmission in relation to site visits is overall considered to be low, however this may vary between geographical areas. For site visits and travel to sites, participants should follow local guidance and recommendations of regional health authorities, such as masking and social distancing, to minimize the risk of exposure to COVID-19.

#### 6.3.1.2 COVID-19 Vaccination

The effect of study drug on efficacy of any vaccine is unknown. The aim of the study drug is to induce local, antigen specific tolerance to impact islet autoimmunity and beta cell destruction. The study drug is administered subcutaneously into the abdomen with effects in draining lymph nodes. There is no evidence of systemic tolerance from pre-clinical models of study drug. However, there is a theoretical possibility that simultaneous administration of a new antigen, such as COVID-19 vaccination could, through cross-presentation, lead to tolerization to that antigen (such as the COVID-19 spike protein). To mitigate this risk, study drug administration will be separated from COVID-19 vaccination both in space (subcutaneous injection in abdomen for study drug and deltoid for COVID-19 vaccine), and in time (as described below).

Similarly, the COVID-19 vaccine may impact the study by introducing AE's associated with COVID-19 vaccination rather than study medication and by impact on the immune measures tested in the study.

Participants will be instruction to inform the study team of plans to receive COVID-19 vaccination. To address both the potential risk of study drug on the COVID-19 vaccine and the impact of the COVID-19 vaccine on study drug:

- Due to the potential severity of COVID-19 infection, COVID-19 vaccination will be required for all participants including booster vaccination if eligible. Should further future booster vaccination become available it will be recommended to all.
- Documentation of COVID-19 vaccination will be requested from participants.
- Participants are to complete the COVID-19 vaccine series or single dose vaccine and eligible boosters at least two weeks prior to randomization. If participants have access to both a mRNA based vaccine or viral vector vaccine, it is recommended the participant be administered mRNA COVID-19 vaccines.
- Participants who screened for the trial prior to the requirement of COVID-19 vaccination (*Protocol V2.0 05Jan2021*) are able to receive the vaccine during the 12-week period of study drug administration but must wait 3 days from

last study drug dose before getting COVID-19 vaccination. They will receive no further study medication, but will continue on study for safety and mechanistic follow-up. Participants who have completed the 12-week course of study drug may receive vaccine 3 days after last dose of study drug. They will continue on study schedule.

5. If future recommendations are issued by the CDC regarding booster vaccinations, participants are able to receive the booster vaccination at least 3 days after their 12-week course of study drug. Participants who wish to obtain a future COVID-19 booster vaccination during the treatment phase will wait 3 days from last dose of study drug, will receive no further study medication but will continue on study for safety and mechanistic follow-up.

### 6.3.2 General precautions

Subjects will not be enrolled who have other serious active medical problems aside from type 1 diabetes. Frequent monitoring of subjects' medical history, physical examinations, and laboratory studies will allow for early identification of adverse events. All participants will be required to have adequate hemoglobin to allow safe frequent venipuncture. Every attempt will be made to minimize the number of venipunctures.

Subjects will be counseled about the need to report any change in health status between or at the time of visits. Directed questioning about concurrent illness will occur before each injection. No injection will occur in those with signs or symptoms indicative of active infection.

All initial study drug injections will take place in a facility that has resuscitation capabilities and subjects will be closely monitored during and after the injection.

#### 6.4 Pregnancy

Male subjects who are sexually active will be instructed to use condoms from randomization until 3 months post last administration of study drug to assure safety. Female subjects with reproductive potential will be instructed to use highly effective means of birth control (which includes abstinence) from randomization until 3 months post last administration of study drug to assure safety. Female subjects will also be asked to avoid pregnancy until last scheduled study visit at 12 months post randomization. This is to assure accurate endpoint measurements. They will undergo urine pregnancy testing at the start of every study visit. All pregnancies that are identified during the study must be followed to conclusion and the outcome of each must be reported. The investigator should be informed immediately of any pregnancy occurring in a female participant. Pregnancy will be reported by sites to the TrialNet Coordinating Center, who will provide this information to the TrialNet Medical Monitor, DSMB, and Novo Nordisk Trial Safety Group. Monitoring of the participant should continue until the conclusion of the pregnancy. Subjects who are found to be pregnant while on this study shall have treatment withdrawn, but will still be followed for safety and other study measures as appropriate. Treatment will not be resumed. If a participant who was previously sexually inactive becomes sexually active, the participant will be counseled about the need to use a reliable form of birth control.

### 6.5 Hypersensitivity or Anaphylaxis

Individuals with a history of severe reactions to previous vaccinations will be excluded from the study. All visits will occur on a clinical research center or equivalent facility with equipment and staff trained to recognize and treat signs and symptoms of hypersensitivity or anaphylaxis reactions. All individuals will be monitored for reactions for 48 hours on-site after the first dose. The length of the observation time (48 hours) has been chosen based on the predicted Tmax of less than 24 hours for the plasmid encoded proteins and it is anticipated that 48 hours is sufficiently long time to observe any acute adverse events possibly related to Tmax. For the subsequent 4 doses, individuals will be monitored for 4 hours on-site, and for the remaining doses, for 2 hours on-site. Additionally, any individual with signs and symptoms of hypersensitivity or anaphylaxis reaction will be monitored for 8 hours and discharged only if stable with no further evidence of reactions. Individuals that are not stable after 8 hours will be admitted for appropriate medical care and further observation.

#### 7 ADVERSE EVENT REPORTING AND SAFETY MONITORING

#### 7.1 Adverse Event Definition

#### 7.1.1 Adverse Event

In this clinical trial, an adverse event is any occurrence or worsening of an undesirable or unintended sign, symptom or disease whether or not associated with the treatment and study procedures.

From study start through visit 15, the investigator must record all adverse events which are Grade 1 or greater per the NCI CTCAE (see Section 7.1.5. Grading Event Severity below), except for events related to hypoglycemia or hyperglycemia. Hypoglycemia and hyperglycemia should be recorded as adverse events only in the case of requiring the assistance of others due to loss of consciousness or DKA. After visit 15 only grade two or higher AEs are to be recorded (visits 16 & 17).

All SAEs must be recorded throughout the study (from signing of informed consent through visit 17).

The investigator should treat participants with adverse events appropriately and observe them at suitable intervals until the events resolve or stabilize.

Adverse events may be discovered through:

- observation of the participant;
- questioning the participant;
- unsolicited complaint by the participant.

Questioning of the participant should be conducted in an objective manner.

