#### Studies in Primates

Dose toxicity studies in non-human primates to support the FHD trial have been conducted for which full information is available in the investigator brochure.

Protocol Version: Jan 7, 2022

A 4-week dose range finding study with 4 weeks recovery in cynomolgus monkeys has been completed. In addition to standard toxicity endpoints, C-peptide levels, as well as immune endpoints including cytokine panels, immunophenotyping, and dsDNA and IL-2 DIA analysis was investigated. The study also included an assessment of biodistribution of the plasmid.

There were no adverse treatment related effects on any of the measured toxicity parameters and no meaningful changes in concentrations of any of the cytokines measured during the study compared to pre-treatment values. Plasmid was primarily distributed to skin at injection sites and draining lymph nodes and levels declined in the recovery period.

A 13-week toxicity study with recovery also in cynomolgus monkeys has been completed.

In conclusion, subcutaneous injections of NNC0361-0041 at dose levels up to 20 mg once weekly for 13 weeks was well tolerated in cynomolgus monkeys, with only non-adverse findings noted. These comprised high neutrophil counts and mononuclear cell infiltration at injection sites following dosing with 20 mg once weekly with full recovery at 8- and 13-weeks post-end of treatment. The NOAEL was considered to be 20 mg/once weekly (highest administered dose).

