# 7.1.5 Grading Event Severity and Causality

TrialNet has adopted usage of the National Cancer Institute (NCI) Common Technology Criteria for Adverse Events (CTCAE) and/or study-specific criteria for classification to describe the severity of adverse events. TrialNet Investigators will also provide an assessment of relationship of AE to study drug as not, unlikely, possibly, probably, or definitely related.

The CTCAE v5.0 displays Grades 1 through 5 with unique clinical descriptions of severity of each AE based on this general guideline:

- Grade 1: Mild; asymptomatic or mild symptoms; clinical or diagnostic observations only; intervention not indicated.
- Grade 2: Moderate; minimal, local or noninvasive intervention indicated; limiting age appropriate instrumental activities of daily living (ADL)
- Grade 3: Severe or medically significant but not immediately life-threatening; hospitalization or prolongation of hospitalization indicated; disabling; limiting ADL
- Grade 4: Life-threatening consequences; urgent intervention indicated
- · Grade 5: Death related to AE

A semicolon indicates "or" within the description of the grade

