Mechanistic Studies 		X	X		X			X			X					X	X	X	X

A= Individuals will be monitored on-site for 48 hours after dosing with discharge at that time only if stable.

B= Individuals will be monitored on-site for 4 hours after dosing with discharge at that time only if stable. Individuals with any signs or symptoms of hypersensitivity or anaphylaxis will be monitored a minimum of 8 hours with discharge at that time only if stable C= Individuals will be monitored on-site for 2 hours after dosing with discharge at that time only if stable. Individuals with any signs or symptoms of hypersensitivity or anaphylaxis will be monitored a minimum of 8 hours with discharge at that time only if stable

- 1 = Screening: May occur over multiple days as needed
- 2 = Physical Exam: Full exam at screening, and 3 months (visit 14). Directed exam as indicated by medical history or symptoms at other visits as indicated.
- 3 = For visits 16 & 17: Only required to collect SAEs and any grade two or higher AEs; All other visits will report all AEs grade 1 or higher.
- 4 = Covid-19 Assessments will be completed PRN during visits 3-13 based on exposure and symptoms.
- 5 = CGM data from participants who currently use these devices as a part of their standard clinic care will be asked to provide this data to assess their diabetes management and insulin use.
- 6 = Viral PCR: All subjects will have serology and PCR for EBV/CMV at screening and visit 15. Samples for viral load will be obtained at other time points to be tested in symptomatic individuals.
- 7 = The following drug-induced antibodies (DIA) will be measured: anti-dsDNA, anti-IL2, anti-IL10, anti-TGFβ. Anti-dsDNA will be measured real-time and collected separately from the other DIAs, which will be tested in batch. Samples collected at dosing visits will be collected pre-dose.
- 8 = Plasmid DNA/RNA samples will be collected at visits 0,1,2,3,6,9,14,15,16,17. At visits 0-2, samples will be collected at the following time points related to Dose 1: Pre-dose and then post-dose at 1h, 8h +/-1h, 12h +/-1h, 24h +/-4h, 48h +/-6h. Samples at V3 and later dosing visits will be collected pre-dose.
- 9 = Cytokine samples to assess safety and mechanism of action will be collected at Visits 0,1,2,3,6,9,14,17. At Visits 0-2, samples will be collected at the following time points related to Dose 1: Pre-dose and then post-dose at 8h +/-1h, 24h +/-4h, 48h +/-6h. Samples at V3 and later doing visits will be collected pre-dose.

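### Injection sites are to be assessed for local reaction and fibrosis at every visit, but the Schedule has no such procedure and a new grade 1 finding after visit 15 is not recorded

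*Protocol*

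**What the plan says.** **Assessment.** Protocol section 6.2.2 warns that "Injection site reactions may also occur" and goes on to say that "injection sites will be carefully assessed for local reaction and fibrosis at each study visit". The Schedule of Assessments has no injection-site row. Its nearest item is the physical exam, which is marked at every visit except visit 1. Footnote 2 defines it: "Full exam at screening, and 3 months (visit 14"), and otherwise "Directed exam as indicated by medical history or symptoms at other visits as indicated".

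**Recording.** Section 7.1.1 sets two thresholds. Up to visit 15: "From study start through visit 15, the investigator must record all adverse events which are Grade 1 or greater". Later: "After visit 15 only grade two or higher AEs are to be recorded (visits 16 & 17"). SAEs are recorded throughout. Schedule footnote 3 and SAP 8.2.2 carry the same limit for visits 16 and 17. The general guideline in 7.1.5 describes the lowest grade as "Grade 1: Mild; asymptomatic or mild symptoms; clinical or diagnostic observations only; intervention not indicated".

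**Follow-up and data capture.** Section 7.1.1 also has the investigator keep adverse events under observation until they have cleared or are no longer changing. Section 7.2 asks for outcome information, and for extra detail on any injection site reaction in a dedicated CRF section.

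**Animal data.** The 13-week monkey study found high neutrophil counts and mononuclear cell infiltration at injection sites at 20 mg weekly, classed as non-adverse, "with full recovery at 8- and 13-weeks post-end of treatment".

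**The concern.** Section 6.2.2 sets an assessment at every visit, visits 16 and 17 included. A site that works from the Schedule can complete each visit correctly without inspecting a symptom-free injection site at most of them. If it does inspect, and finds a small painless induration for the first time at month 6 or 12, the recording rule tells it not to enter the finding. The plan asks for an observation and then gives it nowhere to go.

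This is a first-in-human, ascending-dose trial whose primary objective is safety and tolerability. Local exposure rises by cohort: cohort 4 receives three injections per dose, so 3 x 12 = 36 over a full course, against 12 in cohort 1. Section 6.1.4 notes that excess TGF-β1 can cause tissue remodeling, and the primate section says that the plasmid was found mainly in skin at injection sites and in draining lymph nodes. If no late mild local findings are reported, a reader could not tell absence from non-recording.

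**Working it through.** The plan states no figure of its own on this point. The check is date arithmetic on the Schedule, followed by a comparison of the rules.

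**Inputs**
- Dose 12: visit 13, day 77, window +/- 1 day (section 5.5 and Schedule)
- Visit 15: day 120, window +/- 3 days (section 5.5 and Schedule), but +/- 14 days in section 8.3 and SAP 6.2
- Visit 16: day 180. Visit 17: day 365

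**Time from last dose to the end of grade 1 recording**
- On target: 120 - 77 = 43 days; 43 / 7 = 6.1 weeks
- Earliest, with section 5.5 windows: (120 - 3) - (77 + 1) = 39 days = 5.6 weeks
- Latest: (120 + 3) - (77 - 1) = 47 days = 6.7 weeks
- With the section 8.3 window: (120 - 14) - 78 = 28 days (4.0 weeks) to (120 + 14) - 76 = 58 days (8.3 weeks)

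The Schedule's own week row gives 16 - 11 = 5 weeks, because it labels day 120 as week 16 although 120 / 7 = 17.1.

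These figures are for participants who receive dose 12. With an earlier last dose the interval to visit 15 is longer: 120 - 63 = 57 days (8.1 weeks) if the last dose was dose 10.

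**What comes after**
- Visit 16: 180 - 77 = 103 days (14.7 weeks) after dose 12, grade 2 or higher only
- Visit 17: 365 - 77 = 288 days (41.1 weeks), same limit
- Period in which a new grade 1 finding is not recorded: 365 - 120 = 245 days, 67% of the 365-day follow-up

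**The rules side by side, for a grade 1 local finding**
- First noticed up to visit 15: assessed under 6.2.2, recorded under 7.1.1, followed until it clears or is stable, with outcome reported under 7.2. No gap in the recording rule, but no Schedule item prompts the inspection.
- First noticed at visit 16 or 17: assessed under 6.2.2, not recorded under 7.1.1, footnote 3 or SAP 8.2.2. The injection-site CRF section is described within adverse event reporting, so nothing clearly triggers it either.

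**The case against.** The best defense is that 6.2.2 is binding text, which a footnote about general physical exams does not cancel. A directed exam can include the injection site, and the exam row is marked at every visit but visit 1. That visit falls within the 48-hour inpatient stay, with adverse events assessed that day and exams marked at visits 0 and 2. Section 6 lists injection site reaction data among the material for the sentinel reviews. The grade 1 limit is also consistent: the on-treatment period and the primary endpoint both end at visit 15, so later events lie outside the primary endpoint by definition.

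Much of this stands. A reader might infer from the Schedule that injection sites are not looked at except at visit 14; 6.2.2 says otherwise, and the CRF is not among the documents. A reader might also infer that persisting mild fibrosis is lost after visit 15; 7.1.1 and 7.2 require an event already recorded to be followed and its outcome reported.

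The monkey data tempt a third inference: that grade 1 recording stops too early because recovery was shown at 8 and 13 weeks (days 133 and 168, counted from dose 12). The documents do not support that. The finding was non-adverse cell infiltration, not fibrosis. Those weeks are the preset points at which recovery was checked. They show neither how long recovery took nor any late onset, and they set no surveillance period for people.

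The defense does not explain why 6.2.2 requires an assessment at visits 16 and 17 whose mild results may not be recorded, or why an every-visit assessment is missing from the table that lists procedures by visit.

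**Conclusion.** The conflict is real and narrow. Section 6.2.2 and the Schedule disagree on whether injection-site assessment is a procedure at each visit. Section 6.2.2 and the grade limit in 7.1.1, footnote 3 and SAP 8.2.2 disagree on what happens to a mild finding first seen after visit 15. What is lost is the record of new or newly noticed grade 1 local findings at two visits, from about 6 weeks after dose 12 (39 to 47 days under section 5.5) to month 12. Grade 2 or higher events and SAEs are kept, and the primary endpoint count does not depend on the cut-off.

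Two assumptions matter. Symptom-free induration or fibrosis is taken as grade 1 under the general guideline in 7.1.5; the term-specific CTCAE grade and any study-specific criteria are not in the documents. The interval figures assume that dose 12 was given.

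This is a cheap improvement to the local tolerability data, not a flaw that undermines the trial's main result.

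**What to change.** - Add an injection-site assessment row (local reaction and fibrosis) to the Schedule of Assessments at each study visit, including visit 1, to match 6.2.2.
- In 7.1.1, footnote 3 and SAP 8.2.2, exempt injection-site findings from the grade 2 limit at visits 16 and 17. Record new or persisting findings of any grade on the existing injection-site section of the CRF.
- Include these records in summaries already planned. SAP 6.1 covers severity and outcome over the whole trial. The by-dose summary in SAP 8.2.2 stands under the on-treatment heading, so one sentence should extend it to injection-site findings after visit 15. The primary endpoint definition stays as it is.
- Reconcile the visit 15 window: +/- 3 days in section 5.5 and the Schedule, +/- 14 days in section 8.3 and SAP 6.2. Align the day 120 and week 16 labels at the same time.

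The cost is wording changes in the protocol, Schedule and SAP, a brief check at existing visits, and a few more grade 1 records at visits 16 and 17. No visit or laboratory test is added.
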